## 5 Number of Participants

Indicate the total number of participants to be recruited and enrolled: 20

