**SOCIAL BEHAVIORAL INSTRUCTIONS AND TEMPLATE**

NUMBER	DATE	PAGE
HRP-503a	12/21/2017	3 of 6

This 10-week study has 2 main parts: (A) an EMA study and (B) a Screening experiment. Twenty participants will be recruited for the study.

Prior to the start of the study, participants will first have to complete an initial online screening survey to determine eligibility. All eligible participants will be requested to complete an online consent and depending on their smartphone operating system, will be sent instructions (see appendix D, E, F, and G) on how to download the smartphone apps that will be used in the study:

Smartphone App	OS	Description
PACO	Android or iOS	An open-source app designed that will be used to deliver EMA questions randomly throughout a participant's workday.
Daynamica	Android	An app designed to collect user activity and travel data using raw smartphone accelerometer and GOS data.
Prox	iOS	An iOS app designed to capture real-time indoor (office) location through proximity sensors deployed around the workplace.

Eligible and consented participants will be invited to a one-hour orientation session where they will be given detailed information about the study, along with answering any questions or concerns they may have. During this visit, proximity sensors will also be deployed to various key areas in the workplace (i.e., participant's desk, lobby, kitchen, and conference rooms).

Timeline:

	Week									
	Part A				Part B					
Measures	1	2	3	4	5	6	7	8	9	10
Main Survey	X						X			X
Daily logs	X	X	X	X			X	X	X	X
EMA	X	X	X	X						
Prompts							X	X	X	X
ActivPAL	X	X	X	X			X	X	X	X

Throughout Parts A and B (weeks 1-10):

All participants in both part A and B will be asked to complete daily logs that will ask them of the time they went to work and got off of work the previous day, sleep time of the previous night and the time they woke up, and any work-related meetings that they had the previous day. In addition, they will be asked to complete a battery of assessment (see appendix A for list of questionnaires) at three time points in the study: at week 1, 7, and 10. Participants will also be asked to wear the activPAL device on their thigh as an objective measure of sedentary and physical activities. They will be asked to wear the device continuously throughout the study except for the interview weeks (week 5 and 6). The activPAL will be dropped off every Monday morning and picked up every Friday of the same week.

Part A (Weeks 1-4):

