**Part B (weeks 5-9):**

Participants will be randomized to either receive or not to receive prompts every work hour (8 per day) via email, for 4 weeks. A total of 80 prompts will be sent to participants over a 4-week period during their work hours (9AM-5PM) on workdays.

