### *PART B*

For instances where prompts were sent and a response occurred, the response time will be recorded (seconds) and the average response time calculated. The number of responses occurring each hour will be calculated to identify the frequency of responses by hour. Generalized estimating equations (GEEs) will be ran using GENMOD (with a repeated statement) to examine the main effect of prompt delivery (sent or not sent) by modeling the mean likelihood of a response as an odds ratio, over the next 5-minute and 30-minute periods. An autoregressive model will be used to account for time dependency and the correlation between observations. Mixed model analyses will be conducted using PROC MIXED to examine the association between prompt type and total sedentary time over the next 5-minute and 30-minute period. All models will be adjusted for age, race, gender, day of intervention and minutes of sitting 30 minutes prior to a prompt. Decision points where the participant was standing or moving at the time of prompt delivery (sent) or scheduled (not sent) time will be excluded from analyses.

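### Part B screens decision points on posture alone; work start and end times, already logged daily, could remove seated points outside actual work time

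*SAP*

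**What the plan says.** **Decision points follow the clock.** Protocol section 7, Part B: "Participants will be randomized to either receive or not to receive prompts every work hour (8 per day) via email, for 4 weeks". It then gives the count and the window: "A total of 80 prompts will be sent to participants over a 4-week period during their work hours (9AM-5PM) on workdays". The fixed window is equated with the participants' own work hours.

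**The SAP has one filter, and it is posture.** Statistical analyses, PART B: "Decision points where the participant was standing or moving at the time of prompt delivery (sent) or scheduled (not sent) time will be excluded". The stated covariates are three demographic factors, study day and sitting in the preceding half hour. Neither being at work nor the log appears as an exclusion, covariate or sensitivity analysis.

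**Actual work times are recorded.** Protocol section 7: "All participants in both part A and B will be asked to complete daily logs". These are "daily logs that will ask them of the time they went to work and got off of work the previous day". The timeline table marks the logs in weeks 7 to 10, the same weeks as the prompts.

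**The device records away from the desk.** The same section has the activPAL worn continuously, delivered on Monday and collected on Friday of each study week, so a sitting reading can exist when the person is not at work.

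**The concern.** The posture filter is an availability rule: someone already standing or moving cannot make the sit-to-stand change that is the primary outcome. The same thinking applies to someone who is seated but not at work, for whom a work-hours prompt may do little or nothing. Such a person passes the SAP's filter.

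If prompts work less well at those points, mixing them in moves the estimated effect toward no effect and lowers the chance of detecting a real one, in a study of 20 people. The data needed to identify the points are already being collected. If the SAP stays silent, the analyst must either keep them as written or decide after seeing the data whether to drop them.

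**Working it through.** **Inputs from the documents.** 8 decision points per workday, 4 weeks, 80 prompts (Protocol section 7, Part B); 20 participants (section 5).

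**The plan's own count.** 8 × 5 days × 4 weeks = 160 decision points per participant. Half of 160 is 80, which matches the stated number of prompts if the chance of sending is 0.5 (inferred, not stated). In total, 160 × 20 = 3,200.

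**Which weeks.** The timeline puts prompts and logs together in weeks 7 to 10. The Part B heading says weeks 5 to 9. These passages need reconciling; log coverage is read here from the timeline.

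**Inputs that are assumed.** The documents give no response rates, effect size, power, alpha or off-work share. Let *f* be the share of retained seated points that are off work. Assume 5-minute response rates at work of 20% (not sent) and 30% (sent), and 20% off work in both conditions.

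**Dilution.** Sent rate = (1 − f) × 0.30 + f × 0.20. Risk difference = (1 − f) × 10 points. Odds ratio = [sent rate / (1 − sent rate)] / (0.20/0.80).

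**Information.** This is roughly the number of points times the squared risk difference. Relative to f = 0, keeping the points gives (1 − f)² and dropping them gives (1 − f).

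| f | Sent rate | Risk difference (points) | Odds ratio | Information, kept | Information, dropped |
|---|---|---|---|---|---|
| 0 | 30.0% | 10.0 | 1.71 | 100% | 100% |
| 5% | 29.5% | 9.5 | 1.67 | 90% | 95% |
| 10% | 29.0% | 9.0 | 1.63 | 81% | 90% |
| 20% | 28.0% | 8.0 | 1.56 | 64% | 80% |
| 30% | 27.0% | 7.0 | 1.48 | 49% | 70% |

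**Power, for illustration.** A separate calculation assumes 20% versus 28%, 800 seated points per condition (half of 1,600), a design effect of 2 and a two-sided 0.05 test. Power is 76% at f = 0. Kept versus dropped, it is 71% and 73% at f = 5%, 67% and 71% at 10%, 57% and 66% at 20%, and 47% and 60% at 30%.

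**Different off-work baseline.** Suppose the off-work rate is 10% instead of 20%, with f = 10%. The rates are 0.9 × 0.20 + 0.1 × 0.10 = 19% and 0.9 × 0.30 + 0.1 × 0.10 = 28%. The difference is still 9 points, and the odds ratio is (0.28/0.72)/(0.19/0.81) = 1.66.

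**Partial off-work effect.** Suppose the off-work risk difference is a fraction *g* of the at-work one. The overall difference is then multiplied by 1 − f(1 − g). Keeping the points gives information [1 − f(1 − g)]², against (1 − f) for dropping them. At f = 10% and g = 0.5 this is 0.95² = 0.90 against 0.90, which is break-even. Any g below 1 attenuates the at-work estimate, but dropping the points gains power only if g is below about one half.

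**The case against.** - **Off-work points may be rare.** The protocol calls the window the participants' work hours, on workdays, so leave is arguably outside the design. Entry requires full-time work with more than 7 hours a day sedentary at work. For someone working 9 to 5, that leaves under 1 hour in 8 (12.5%) of a typical day. This stands as a reason to expect a small share and to give the 20% and 30% rows little weight. It is not a bound: shifts may be offset from the clock window, and a typical day says nothing about absences.
- **An e-mail can be read off site.** The protocol says only that prompts go by e-mail, and participants carry smartphones. This stands: a zero off-work effect is an assumption, and the power gain needs an off-work effect below about half of that at work.
- **The planned analysis has a legitimate target.** It estimates the effect of sending a scheduled prompt to a seated person. This stands, and is why that analysis should still be reported. The protocol's own wording, however, points to work time.
- **Not every point is kept.** Points without activPAL data, such as those before Monday delivery or after Friday collection, drop out anyway. That removes non-wear, not off-work wear.
- **The logs are self-report made after randomisation.** Recall error is real. The rule treats sent and not-sent points alike, and the sensitivity analysis shows whether it matters.

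A reader might also infer that logged meetings should be used, since the log asks about "any work-related meetings that they had the previous day". The documents do not support that. Meetings are work time, so they are not a source of off-work dilution, and the protocol does not say that meeting clock times are recorded. A point-level meeting indicator may not be constructible.

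**Conclusion.** The point holds as a cheap improvement to the analysis. Posture is the only stated filter, and work start and end times are collected in the prompt weeks but unused, so a seated, device-wearing participant outside actual work time is retained.

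A reader might infer that off-work points do dilute the effect, or that the planned test is invalid. The documents support neither. They do not show that such points occur or how often, so the size runs from nil upward. Since sending is randomised, keeping the points does not bias the test under the null or inflate the type I error; it costs sensitivity and changes what is estimated.

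If the off-work effect is zero, the risk difference shrinks by exactly the off-work share. At shares of 5% to 10%, with the assumed 20% and 30%, the odds ratio moves from 1.71 to between 1.67 and 1.63. In the separate power illustration, dropping the points recovers about 2 to 4 percentage points. These figures rest on assumed rates and ignore the planned covariate adjustment.

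**What to change.** Add to the PART B analysis section of the SAP:

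> In addition to the posture rule, a decision point is eligible for the main analysis only if it lies between the logged start and end of work on a day worked. The rule applies identically to sent and not-sent points. Where the log is missing, the participant is treated as at work. The analysis of all sitting decision points is reported as a sensitivity analysis.

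Report the number of points removed by the rule in each condition and the number retained because of a missing log. Do not add a meeting covariate.

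The cost is SAP wording and a merge of data already collected, with no added participant burden. The downsides are a small loss of records and reliance on next-day self-report. Because missing logs count as at work, a leave day is removed only if its log was completed and shows no work; some off-work points may therefore remain.
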